5.3 Timing of Dose Administration

For Group A pre-surgery, participants will receive a single infusion of pembrolizumab 200mg 14 +/- 5 days prior to scheduled surgical resection (when scheduling, please keep in mind that the two pre-surgical plasma samples should be drawn greater than 10 days apart - see Table 6 for full details) .

For Group A and B after recovery from surgery (once participant has recovered from surgery, but no more than 35 days following surgery), trial treatment should be administered on Days 1 and 22 of each 6 week cycle after all procedures/assessments have been completed and reviewed as detailed on the Trial Flow Chart (Section 9). Trial treatment may be administered up to 3 days before or after the scheduled day of each cycle due to administrative reasons.

All trial treatments will be administered on an outpatient basis.

Pembrolizumab 200 mg will be administered as a 30 minute IV infusion every 3 weeks. Sites should make every effort to target infusion timing to be as close to 30 minutes as possible.

However, given the variability of infusion pumps from site to site, a window of -5 minutes and +10 minutes is permitted (i.e., infusion time is 30 minutes: -5 min/+10 min).

The Pharmacy Manual contains specific instructions for the preparation of the pembrolizumab infusion fluid and administration of infusion solution.

5.4 Trial Blinding/Masking

This is an open-label trial; therefore, the Sponsor, investigators and subject will know the treatment administered.

5.5 Stratification

No stratification based on age, gender or other characteristic will be used in this trial.

5.6 Patient Evaluability and Replacement

See protocol section 12.2.5 Analysis Population.

If a participant is enrolled to trial and local pathology from the on-study surgery is unable to definitively confirm recurrent tumor, then the participant will be considered non-evaluable for primary and secondary endpoints, but may continue to receive study treatment per protocol. In these instances, please contact the DFCI Coordinating Center as soon as possible to obtain Sponsor-Investigator and manufacturer approval.

5.7 General Concomitant Medication and Supportive Care Guidelines

Medications or vaccinations specifically prohibited in the exclusion criteria (Section 3.2) are not allowed during the ongoing trial except as outlined below. If there is a clinical indication for one of these or other medications or vaccinations specifically prohibited during the trial, discontinuation from trial therapy or vaccination may be required. The treating investigator should discuss any questions regarding this with the sponsor and the overall study PI or his designee. The final decision on any supportive therapy or vaccination rests with the treating. However, the decision to continue the subject on trial therapy or vaccination schedule requires the mutual agreement of the Investigator, Sponsor, overall study PI or his designee, and the subject.

5.7.1 Acceptable Concomitant Medications

All treatments that the investigator considers necessary for a subject's welfare may be administered at the discretion of the investigator in keeping with the community standards of medical care. All concomitant medication will be recorded on the case report form (CRF) including all prescription, over-the-counter (OTC), herbal supplements, and IV medications and fluids. If changes occur during the trial period, documentation of drug dosage, frequency, route, and date may also be included on the CRF, when information is available.

All concomitant medications received from date of consent up to 30 days after the last dose of trial treatment should be recorded. Concomitant medications administered after 30 days after the last dose of trial treatment should be recorded for SAEs and ECIs.

5.7.2 Prohibited Concomitant Medications

Subjects are prohibited from receiving the following therapies during the Screening and Treatment Phase of this trial:

- Anti-cancer systemic chemotherapy or biological therapy, with the exception of bevacizumab for the purpose of symptomatic management or to control cerebral edema (see section 5.8)
- Immunotherapy not specified in this protocol
- Chemotherapy not specified in this protocol
- Investigational agents other than pembrolizumab

- Radiation therapy
- Live vaccines within 30 days prior to the first dose of trial treatment and while participating in the trial. Examples of live vaccines include, but are not limited to, the following: measles, mumps, rubella, varicella/zoster, yellow fever, rabies, BCG, and typhoid vaccine.
- Systemic glucocorticoids for any purpose other than to modulate symptoms from an event of clinical interest of suspected immunologic etiology or to control cerebral edema. The use of physiologic doses of corticosteroids may be approved after consultation with the Sponsor and Overall PI, [name].
- Subjects who, in the assessment by the investigator, require the use of any of the aforementioned treatments for clinical management should be removed from the trial. Subjects may receive other medications that the investigator deems to be medically necessary.

There are no prohibited therapies during the Post-Treatment Follow-up Phase.

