5.8.1 Cerebral Edema

Due to the immunologic nature of pembrolizumab administration, cerebral edema could theoretically result as a consequence of pembrolizumab administration due to immune infiltration of the brain. Symptoms related to cerebral edema may include headache or neurologic deficits that are either new or worsened. Patients with any signs or symptoms of cerebral edema should be treated as clinically appropriate including initiation or increased systemic corticosteroid dosing, initiation of bevacizumab administered per local institutional practice, treatment with an osmotic diuretic or surgical decompression. An investigator may initiate bevacizumab per local institutional practice if significant mass effect is seen on an MRI in anticipation of subsequent clinical decline. Subsequent pembrolizumab dosing should be immediately interrupted if significant clinical symptoms attributable to cerebral edema develop. Treatment with additional pembrolizumab doses may only be re-initiated if clinically significant symptoms attributable to cerebral edema have resolved to grade ≤ 1 or pre-treatment baseline. Patients who develop CTCAE 5.0 grade 4 cerebral edema attributable to pembrolizumab administration should not receive further pembrolizumab doses and should discontinue study therapy.

NOTE: every effort should be made to not exceed a corticosteroid dose of > 4 mg / day between date of registration and on-study surgery. If a corticosteroid of > 4 mg / day is necessary a participant following registration and prior to on-study surgery, the treating investigator should reach out to the Overall PI to confirm the participant's evaluability for tumor tissue studies.

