- c) Clear clinical deterioration not attributable to other causes apart from the tumor (e.g. seizures, medication side effects, complications of therapy, cerebrovascular events, infection, etc.). The definition of clinical deterioration is left to the discretion of the investigator but it is recommended that a decline in the Karnofsky Performance Score (KPS) from 100 or 90 to 70 or less, a decline in KPS of at least 20 from 80 or less, or a decline in KPS from any baseline to 50 or less, for at least 7 days, be considered neurologic deterioration, unless attributable to co-morbid events or changes in corticosteroid dose.
- d) Failure to return for evaluation due to death or deteriorating condition

10.2.4 Stable disease (SD). All of the following criteria must be met:

- a) Does not qualify for CR, PR, or progression.
- b) All measurable and non-measurable sites must be assessed using the same techniques as baseline.
- c) Stable clinically.

10.2.5 Unknown response status. Progressive disease has not been documented and one or more measurable or non-measurable lesions have not been assessed.

The RANO Response Criteria to be used in this study are summarized in Table 7.

Table 7 Summary of the RANO Response Criteria

	CR	PR	SD	PD#
T1-Gd +	None	$\geq 50\%$ decrease	$<50\%$ decrease- $<25\%$ increase	$\geq 25\%$ increase*
T2/FLAIR	Stable or decrease	Stable or decrease	NA	NA
New Lesion	None	None	None	Present*
Corticosteroids	None	Stable or decrease	Stable or decrease	Stable or increasing
Clinical Status	Stable or increase	Stable or increase	Stable or increase	Decrease*
Requirement for Response	All	All	All	Any*

CR=complete response; PR=partial response; SD=stable disease; PD=progressive disease;
NA= not applicable

#: Progression occurs when any of the criteria with * is present

Increase in corticosteroids alone will not be taken into account in determining progression in the absence of persistent clinical deterioration

Of note, patients who require increased corticosteroids within two weeks of MRI assessment (relative to the dose taken at the time of the prior assessment) cannot be classified as CR, PR or SD and should be classified as non-evaluable at that time point. Conversely, patients who decrease corticosteroids within two weeks of MRI assessment (relative to the dose taken at the time of the prior assessment) cannot be classified as PD and should be classified as non-evaluable.

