- Tumor Enhancement to Define Progression: RANO expanded the previously utilized Macdonald criteria¹⁰⁶ to include the development of “significantly” increased T2 or FLAIR abnormality in the definition of progressive disease because such changes can be a major component defining radiographic progression following therapeutic use of VEGF/VEGFR-targeting therapeutics which are known to elicit potent anti-permeability changes that limit contrast uptake. However, immune based therapies are expected to be associated with inflammatory changes that may include edema. Therefore, radiographic progressive disease will be defined by assessment of enhancing tumor and will not declare tumor progression based on the presence of T2 or FLAIR changes alone as outlined in RANO because:
 - There is no expectation that immunotherapy agents including PD-1 inhibitors will falsely diminish enhancing tumor burden as has been noted with anti-angiogenic therapies; and
 - Immune based therapies are expected to induce inflammatory responses which may be associated with increased edema and T2/FLAIR changes. Such radiographic finding may inaccurately be interpreted to represent tumor progression (i.e. pseudoprogression).

In subjects who have initial evidence of radiographic PD, it is at the discretion of the treating physician whether to continue a subject on study treatment for up to three months pending

confirmation of PD on follow-up imaging. This clinical judgment decision should be based on the subject's overall clinical condition, including performance status, clinical symptoms, and laboratory data. Subjects may receive study treatment while waiting for confirmation of PD if they are not experiencing significant clinical decline and the subject is adequately tolerating study therapy (if a subject is required to discontinue study treatment for toxicity as defined per protocol section 5, then they must be taken off-treatment).

When feasible, study therapy should not be discontinued until radiographic progression is confirmed. This allowance to continue treatment despite initial radiologic progression takes into account the observation that some subjects can have a transient tumor flare in the first few months after the start of immunotherapy, but with subsequent disease response.¹⁰⁵ Subjects that are exhibiting significant neurologic decline are not required to have repeat imaging for confirmation of progressive disease.

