12.2.6.1 Statistical Methods for Primary Endpoint and Efficacy Analyses

Stage 1:

A two-sample Student's t-test will be used to test the difference of TIL density between the two groups. Data distribution will be examined prior to analysis. Data transformations will be performed as deemed appropriate.

Stage 2:

A two-sample Student's t-test will be used to test the difference of cell cycle-related signature between the two groups. Data distribution will be examined prior to analysis. Data transformations will be performed as deemed appropriate.

For PFS endpoint, the analyses will be conducted using pooled Group A and Group B patients. Kaplan-Meier (KM) curves and median estimates from the KM curves will be provided as appropriate. Percent PFS6 will be estimated from the KM curves and compared to historical controls. Subjects without efficacy evaluation data or without survival data will be censored at Day 1.

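### Bevacizumab is permitted on study, radiographic RANO progression rests on enhancing lesions, and the SAP has no PFS rule for it, so PFS6 can be biased upward by an unknown amount

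*Combined protocol and SAP*

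**What the plan says.** **Permission.** Section 5.7.2 excludes other systemic anti-cancer drugs and biologics during screening and treatment, "with the exception of bevacizumab for the purpose of symptomatic management or to control cerebral edema". Section 5.8.1 lists bevacizumab among the options for cerebral edema and adds: "An investigator may initiate bevacizumab per local institutional practice if significant mass effect is seen on an MRI in anticipation of subsequent clinical decline". It can therefore be started before any clinical criterion for progression is met. Pembrolizumab is interrupted only for significant symptoms and may be restarted when they resolve. Section 3.2.6 excludes prior anti-VEGF treatment, so on-study use is first exposure.

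**Progression.** The radiographic criteria in Section 10.2.3 (a) and (b) concern enhancing lesions, and Table 7 marks T2/FLAIR as not applicable to progression. Section 10.5 gives the reasoning: "radiographic progressive disease will be defined by assessment of enhancing tumor", because PD-1 inhibitors are not expected to "falsely diminish enhancing tumor burden as has been noted with anti-angiogenic therapies". Two further criteria in Section 10.2.3 do not depend on enhancement: "Clear clinical deterioration not attributable to other causes apart from the tumor" and "Failure to return for evaluation due to death or deteriorating condition".

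**Analysis.** PFS6 by RANO is the secondary objective (1.3.1) and the named efficacy endpoint (12.2.4.1). Section 12.2.6.1 pools Groups A and B and states: "Percent PFS6 will be estimated from the KM curves and compared to historical controls". Its only censoring rule sends subjects without data to Day 1.

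**The concern.** The protocol drops T2/FLAIR from radiographic progression because pembrolizumab should not suppress enhancement artificially. That reasoning does not carry over to a patient who is also receiving bevacizumab, the class of drug that Section 10.5 names as having this effect. Such a patient may have growing tumour without growing enhancement, and the analysis has no instruction other than to read the scan as usual.

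PFS6 is the trial's only non-exploratory efficacy endpoint and is judged against an external rate. A masked progression raises the estimate, and the excess would be credited to pembrolizumab. The decision to start bevacizumab lies with the investigator in an open-label trial. If the handling is settled only after the data are seen, it can be chosen with the answer in view.

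**Working it through.** **1. Is there a rule anywhere?**
- Section 12.2.6.1 covers only subjects without data.
- Sections 1.1 and 5.10 mention non-study cancer treatment, but as a point at which disease follow-up stops after treatment has been discontinued. Footnote f of the Study Calendar omits even that stopping point.
- The removal clause in Section 5.7.2 applies to prohibited treatments, and bevacizumab for symptoms or edema is excepted from the prohibition.
- Section 10.2 makes a scan non-evaluable around certain corticosteroid changes. This kind of confounding was recognised, but no counterpart was written for bevacizumab.

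**2. Which progression definition is affected?** Section 10.5 is the exploratory iRANO section, but the point does not depend on it: Section 10.2.3 and Table 7 give the same enhancement basis for RANO. Under iRANO a second route exists. If bevacizumab is started after a first progressive scan, the repeat scan may look stable and progression goes unconfirmed. Section 2.3.3.1 names iRANO for the efficacy endpoints while 1.3.1 and 12.2.4.1 name RANO, so the text should also settle which one governs.

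**3. How sensitive is PFS6?** The documents give no sample size, power or success threshold for PFS6, so there is no stated figure to reproduce. Inputs:
- p = true PFS6 = 10%. Section 2.1 quotes salvage rates under 10%; 10% is taken as the benchmark.
- n = 30 + 20 = 50 evaluable patients (synopsis), all assumed followed to six months.
- f = share starting bevacizumab before progression and before month 6. **Assumption**, 0-40%.
- m = share of starters' progressions before month 6 that go unrecorded. **Assumption**, 10-50%.

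Apparent PFS6 with starts ignored = p + f × m × (1 − p). With every start counted as an event, and starters having the same true PFS6 as the rest, the estimate is p × (1 − f).

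For scale, suppose the result were tested against 10% by exact binomial. The smallest count with upper-tail probability at most 0.05 is 10 of 50 (exact 0.0245). The plan sets no such test.

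| f | m | Starts ignored | Bias (points) | Chance of ≥10/50 | Starts as events |
|---|---|---|---|---|---|
| 0 | any | 10.0% | 0 | 0.025 | 10% |
| 10% | 10% | 10.9% | 0.9 | 0.041 | 9% |
| 20% | 25% | 14.5% | 4.5 | 0.180 | 8% |
| 30% | 25% | 16.75% | 6.75 | 0.323 | 7% |
| 20% | 50% | 19.0% | 9.0 | 0.485 | 8% |
| 40% | 50% | 28.0% | 18.0 | 0.926 | 6% |

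The same model can be written with q, the share of starters scored progression-free at six months: apparent PFS6 = (1 − f) × 10% + f × q. At f = 10%, q = 30% this is 9% + 3% = 12%. At f = 30%, q = 50% it is 7% + 15% = 22%. At q = 10% the bias is zero.

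If bevacizumab only masks progression, the ignore analysis and the event analysis lie on either side of the true value.

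**The case against.** Much of the case against a stronger statement stands.

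- A reader might infer that progression is judged on enhancement alone. It is not: clinical deterioration and death or decline are progression events under Section 10.2.3. Patients given bevacizumab for symptoms may be caught by them.
- A reader might infer that PFS6 is certainly biased. No rate of use is given, and a start after recorded RANO progression cannot change that patient's RANO PFS time. The historical controls are not identified either; whether those patients could receive bevacizumab is unknown.
- A reader might infer that this corrupts the trial's only efficacy result, or a between-group comparison of PFS6. OS, PFS and second PFS are also planned, as exploratory endpoints, and OS does not depend on imaging. PFS6 pools the groups, so unequal use would touch only the exploratory A-versus-B comparison of PFS. Response is not a component of PFS6.
- This is a pilot trial with tissue-based primary endpoints, and Section 12.2.6 calls efficacy p-values nominal.
- Counting every start as progression is not neutral. Section 5.8.1 says that edema may come from immune infiltration due to pembrolizumab, so possible toxicity would be scored as progression. The table shows 6-9% where the truth is 10%.

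The last point rules out the event analysis as the sole answer. None of the points supplies the missing rule.

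**Conclusion.** The gap is real and should be closed before PFS6 is analysed. Bevacizumab is permitted, radiographic RANO progression rests on enhancing lesions, the protocol itself describes how anti-angiogenic drugs distort enhancement, and the PFS analysis is silent. PFS6 run as written can therefore be biased upward.

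The amount is unknown. It is zero if nobody starts bevacizumab before progression or month 6. Over the assumed ranges for starters it is 0.9 to 18 percentage points. The 12-22% range rests on assumed f and q; it shows direction and sensitivity, and the documents do not support reading it as an expected result. The model also attributes the starters' whole excess to masking and leaves out any real delay in progression.

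**What to change.** In Section 12.2.6.1, pre-specify how the start of bevacizumab, or of other non-protocol anti-tumour treatment, before RANO progression is handled. Report PFS6 three ways:

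1. the start counted as a PFS event at its date;
2. censored at the last scan before the start;
3. the start ignored.

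State that the first can understate PFS6 and the third can overstate it. The second assumes that starters would have had the same later risk as other patients, which is doubtful when mass effect prompted the start. Draw a favourable conclusion against historical controls only if it holds across all three.

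Report the number and timing of starts by group. Make the on-treatment bevacizumab start date a required CRF field: Section 5.7.1 has concomitant medication recorded, but says only that dates of changes may be included when available.

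Cost: SAP wording (by protocol amendment, if PFS6 is treated as a key secondary endpoint under Section 12), one CRF field, a little more analysis, and a possibly less favourable PFS6. Nothing here changes who may receive bevacizumab or when.

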5.8 Rescue Medications & Supportive Care

Supportive Care Guidelines

Subjects should receive appropriate supportive care measures as deemed necessary by the treating investigator. Suggested supportive care measures for the management of adverse events with potential immunologic etiology are outlined below. Where appropriate, these guidelines include the use of oral or intravenous treatment with corticosteroids as well as additional anti-inflammatory agents if symptoms do not improve with administration of corticosteroids. Note that several courses of steroid tapering may be necessary as symptoms may worsen when the steroid dose is decreased. For each disorder, attempts should be made to rule out other causes such as metastatic disease or bacterial or viral infection, which might require additional supportive care. The treatment guidelines are intended to be applied when the investigator determines the events to be related to pembrolizumab.

Note: if after the evaluation the event is determined not to be related, the investigator does not need to follow the treatment guidance (as outlined below). Refer to Section 5.2 for dose modification.

It may be necessary to perform conditional procedures such as bronchoscopy, endoscopy, or skin photography as part of evaluation of the event.

- **Pneumonitis:**
 - For **Grade 2 events**, treat with systemic corticosteroids. When symptoms improve to Grade 1 or less, steroid taper should be started and continued over no less than 4 weeks.
 - Recommended corticosteroid regimen:
 - 1-2mg/kg/day prednisone or equivalent

- When symptoms resolve to grade 1 or less, initiate steroid taper for no less than 4 weeks
- For **Grade 3-4 events**, immediately treat with intravenous steroids. Administer additional anti-inflammatory measures, as needed.
 - Recommended corticosteroid regimen:
 - Methylprednisolone 125mg IV daily
 - When symptoms grade 1 or less initiate steroid taper for no less than 4 weeks
 - Prednisone 1-2 mg/kg/day or dexamethasone 4mg every 4 hours
 - If IV steroids do not reduce initial symptoms within 48-72 hours, treat with additional anti-inflammatory measures
 - Add prophylactic antibiotics for opportunistic infections in the case of prolonged steroid administration.
- **Diarrhea/Colitis:**

Subjects should be carefully monitored for signs and symptoms of enterocolitis (such as diarrhea, abdominal pain, blood or mucus in stool, with or without fever) and of bowel perforation (such as peritoneal signs and ileus).

 - All subjects who experience diarrhea/colitis should be advised to drink liberal quantities of clear fluids. If sufficient oral fluid intake is not feasible, fluid and electrolytes should be substituted via IV infusion. For Grade 2 or higher diarrhea, consider GI consultation and endoscopy to confirm or rule out colitis.
 - For **Grade 2 diarrhea/colitis**, administer oral corticosteroids.
 - Recommended corticosteroid regimen:
 - Prednisone 1-2mg/kg/day or equivalent
 - When symptoms grade 1 or less, initiate steroid taper for no less than 4 weeks
 - For **Grade 3 or 4 diarrhea/colitis**, treat with intravenous steroids followed by high dose oral steroids.
 - Recommended corticosteroid regimen:
 - Methylprednisolone 125mg IV daily
 - When symptoms grade 1 or less initiate steroid taper for no less than 4 weeks and in 6-8 weeks in patients with diffuse or severe ulceration and/or bleeding
 - Prednisone 1-2 mg/kg/day or dexamethasone 4mg every 4 hours
 - If IV steroids do not reduce initial symptoms within 48-72 hours treat with additional anti-inflammatory measures
 - When symptoms improve to Grade 1 or less, steroid taper should be started and continued over no less than 4 weeks.

- **Type 1 diabetes mellitus (if new onset, including diabetic ketoacidosis [DKA]) or ≥ Grade 3 Hyperglycemia, if associated with ketosis (ketonuria) or metabolic acidosis (DKA)**
 - For **T1DM** or **Grade 3-4** Hyperglycemia
 - Insulin replacement therapy is recommended for Type I diabetes mellitus and for Grade 3-4 hyperglycemia associated with metabolic acidosis or ketonuria.
 - Evaluate patients with serum glucose and a metabolic panel, urine ketones, glycosylated hemoglobin, and C-peptide.
- **Hypophysitis:**
 - For **Grade 2** events, treat with corticosteroids. When symptoms improve to Grade 1 or less, steroid taper should be started and continued over no less than 4 weeks. Replacement of appropriate hormones may be required as the steroid dose is tapered.
 - For **Grade 3-4** events, treat with an initial dose of IV corticosteroids followed by oral corticosteroids. When symptoms improve to Grade 1 or less, steroid taper should be started and continued over no less than 4 weeks. Replacement of appropriate hormones may be required as the steroid dose is tapered.
- **Hyperthyroidism or Hypothyroidism:**

Thyroid disorders can occur at any time during treatment. Monitor patients for changes in thyroid function (at the start of treatment, periodically during treatment, and as indicated based on clinical evaluation) and for clinical signs and symptoms of thyroid disorders.

 - **Grade 2** hyperthyroidism events (and **Grade 2-4** hypothyroidism):
 - In hyperthyroidism, non-selective beta-blockers (e.g. propranolol) are suggested as initial therapy.
 - In hypothyroidism, thyroid hormone replacement therapy, with levothyroxine or liothyroinine, is indicated per standard of care.
 - **Grade 3-4** hyperthyroidism
 - Treat with an initial dose of IV corticosteroid followed by oral corticosteroids. When symptoms improve to Grade 1 or less, steroid taper should be started and continued over no less than 4 weeks. Replacement of appropriate hormones may be required as the steroid dose is tapered.
- **Hepatic:**
 - For **Grade 2** events, monitor liver function tests more frequently until returned to baseline values (consider weekly).
 - Treat with IV or oral corticosteroids
 - For **Grade 3-4** events, treat with intravenous corticosteroids for 24 to 48 hours.
 - When symptoms improve to Grade 1 or less, a steroid taper should be started and continued over no less than 4 weeks.
- **Renal Failure or Nephritis:**
 - For **Grade 2** events, treat with corticosteroids.

- For **Grade 3-4** events, treat with systemic corticosteroids.
- When symptoms improve to Grade 1 or less, steroid taper should be started and continued over no less than 4 weeks.
- **Management of Infusion Reactions:** Signs and symptoms usually develop during or shortly after drug infusion and generally resolve completely within 24 hours of completion of infusion.

Table 4 below shows treatment guidelines for subjects who experience an infusion reaction associated with administration of pembrolizumab (MK-3475).

Table 4 Infusion Reaction Treatment Guidelines

NCI CTCAE Grade	Treatment	Premedication at subsequent dosing
Grade 1 Mild reaction; infusion interruption not indicated; intervention not indicated	Increase monitoring of vital signs as medically indicated until the subject is deemed medically stable in the opinion of the investigator.	None
Grade 2 Requires infusion interruption but responds promptly to symptomatic treatment (e.g., antihistamines, NSAIDS, narcotics, IV fluids); prophylactic medications indicated for <=24 hrs	
Stop Infusion and monitor symptoms. Additional appropriate medical therapy may include but is not limited to:
 
 IV fluids Antihistamines NSAIDS Acetaminophen Narcotics 
Increase monitoring of vital signs as medically indicated until the subject is deemed medically stable in the opinion of the investigator. If symptoms resolve within one hour of stopping drug infusion, the infusion may be restarted at 50% of the original infusion rate (e.g., from 100 mL/hr to 50 mL/hr). Otherwise dosing will be held until symptoms resolve and the subject should be premedicated for the next scheduled dose.
 
Subjects who develop Grade 2 toxicity despite adequate premedication should be permanently discontinued from further trial treatment administration.
	
Subject may be premedicated 1.5h (\pm 30 minutes) prior to infusion of pembrolizumab (MK-3475) with:
 
Diphenhydramine 50 mg po (or equivalent dose of antihistamine).
 
Acetaminophen 500-1000 mg po (or equivalent dose of antipyretic).

Grades 3 or 4 Grade 3: Prolonged (i.e., not rapidly responsive to symptomatic medication and/or brief interruption of infusion); recurrence of symptoms following initial improvement; hospitalization indicated for other clinical sequelae (e.g., renal impairment, pulmonary infiltrates) Grade 4: Life-threatening; pressor or ventilatory support indicated	
Stop Infusion. Additional appropriate medical therapy may include but is not limited to:
 
 IV fluids Antihistamines NSAIDS Acetaminophen Narcotics Oxygen Pressors Corticosteroids Epinephrine 
Increase monitoring of vital signs as medically indicated until the subject is deemed medically stable in the opinion of the investigator. Hospitalization may be indicated.
 
Subject is permanently discontinued from further trial treatment administration.
	No subsequent dosing
Appropriate resuscitation equipment should be available in the room and a physician readily available during the period of drug administration.		

